**STORAGE CONDITIONS**

[figure not shown]
- Store between 2°C and 25°C.
- Fragile.

**APPENDIX 2      INJECTION SITE REACTION (ISR) 30-DAY DIARY**

**APPENDIX 3 LIP FULLNESS SCALE 2 (LFS2)**

ALLERGAN

## Lip Fullness Scale 2

[figure not shown]

Minimal Flat or nearly flat contour; minimal red lip show
				

Mild Some red lip show; no lower lip pout
				

Moderate Moderate red lip show with slight lower lip pout
				

Marked Significant red lip show and lower lip pout; upper lip with moderate pout
				

Very Marked Very significant red lip show, lower lip pout, and upper lip pout
				

© 2010 Allergan
© 2010 Produced by CANFIELD Scientific, Inc.

Grade	Description
Very Marked	Very significant red lip show, lower lip pout, and upper lip pout
Marked	Significant red lip show and lower lip pout
Moderate	Moderate red lip show with slight lower lip pout
Mild	Some red lip show; no lower lip pout
Minimal	Flat or nearly flat contour, minimal red lip show

[figure not shown]
Clinical Study Protocol: CMO-MA-FAS-0512

**APPENDIX 4 ORAL COMMISSURE SEVERITY SCALE (OCSS)**

Grade	Description
Severe	Very deep and/or long wrinkle or crease; frown at rest
Moderate	Moderately deep and/or long wrinkle or crease; downturned corners
Mild	Shallow, just perceptible wrinkle or crease; horizontal or slightly downturned corners
None	No wrinkle or fold; slight upturned corners

Clinical Study Protocol: CMO-MA-FAS-0512

Clinical Study Protocol: CMO-MA-FAS-0512

**APPENDIX 6 GLOBAL AESTHETIC IMPROVEMENT SCALE (GAIS)**

INVESTIGATOR ASSESSMENT OF GLOBAL AESTHETIC IMPROVEMENT		
Using the Subject's image obtained at Baseline for reference, record your assessment of the level of improvement to the Subject's lips.		
Score (Circle one number)	Grade	Description
2	Much Improved	Marked improvement in appearance
1	Improved	Improvement in appearance, but a touch-up or re-treatment is indicated
0	No Change	The appearance is essentially the same as the original condition
-1	Worse	The appearance is worse than the original condition
-2	Much Worse	The appearance is much worse than the original condition

SUBJECT'S SELF-ASSESSMENT OF GLOBAL AESTHETIC IMPROVEMENT			
While viewing the image of you that was obtained prior to the first study treatment for reference, record your assessment of the level of improvement to your appearance.			
	Score (Circle one number)	Grade	
	2	Much Improved	
	1	Improved	
	0	No Change	
	-1	Worse	
	-2	Much Worse	

Clinical Study Protocol: CMO-MA-FAS-0512

---

**APPENDIX 7      SUBJECT ASSESSMENT OF NATURAL LOOK AND FEEL**

**Please answer the following questions as they relate to your lips NOW after you have been treated.**

Please circle one number for each statement to indicate your agreement with each statement:

	Not at All		Somewhat		Very Much
1. My lips look natural	0	1	2	3	4
2. My lips feel natural	0	1	2	3	4

**APPENDIX 8 INVESTIGATOR ASSESSMENT OF SMOOTHNESS**

**Please answer the following question as they relate to your patient’s lips NOW after they have been treated.**

Please circle one number to indicate the result the product gave to the smoothness of the lips after treatment:

	Lumpy/ Grainy		Somewhat Smooth		Smooth
Smoothness of lips	0	1	2	3	4

**APPENDIX 9 PERIORAL LINES AT REST SEVERITY SCALE (POLSS)**

**APPENDIX 10 INVESTIGATOR ASSESSMENT OF DYNAMIC LIP LINES UPON ANIMATION**

**Please answer the following question as they relate to your patient’s lips NOW after they have been treated.**

Please circle one number to indicate the result the product gave to the dynamic lip lines upon animation (ask the patient to ‘kiss’ lips):

	Worse	No change	Improved	Much improved
Dynamic lip lines upon animation	0	1	3	4

## Revision History

Version #	Date (DD-Mmm-YYYY)	Document Owner	Revision Summary
1.0	09-May-2019	[name]	Initial Release Version
2.0	27-Nov-2019	[name]	Updates for Protocol Version 3 and other minor clarifications

This document is [REDACTED]

[REDACTED]

## 1. Glossary of Abbreviations

Abbreviation	Description
AE	Adverse Event
CTMS	Clinical Trial Management System
DFU	Directions for Use
eCRF	Electronic Case Report Form
ES	Evaluable Set
FAS	Full Analysis Set
GAIS	Global Aesthetic Improvement Scale
HA	Hyaluronic Acid
ICF	Informed Consent Form
ICH	International Conference on Harmonization
IEC	Independent Ethics Committee
IRB	Institutional Review Board
ISR	Injection Site Reaction
LFS2	Lip Fullness Scale
MedDRA	Medical Dictionary for Regulatory Activities
n	Number of Observations
NSAIDs	Non-steroidal Anti-inflammatory Drugs
OCSS	Oral Commissures Severity Scale
PD	Protocol Deviation
pdf	Portable Document Format
POLSS	Perioral Lines Severity Scale
PPS	Per Protocol Set
PT	Preferred Term
SAP	Statistical Analysis Plan
SD	Standard Deviation
SOC	System Organ Class
SOP	Standard Operating Procedure
SS	Safety Analysis Set
TEAE	Treatment-emergent Adverse Event

Abbreviation	Description
TFLs	Tables, Figures and Listings
WHO	World Health Organization

## **2. Purpose**

The purpose of this statistical analysis plan (SAP) is to ensure that the data listings, summary tables and figures which will be produced, and the statistical methodologies that will be used, are complete and appropriate to allow valid conclusions regarding the study objectives.

### **2.1. Responsibilities**

Syneos Health is responsible for the production and quality control of all tables, figures and listings.

### **2.2. Timings of Analyses**

The primary analysis of safety and efficacy is planned after all subjects complete the final study visit or terminate early from the study. An interim analysis will be performed when all patients complete their 6 months visit (or discontinue early).

### **3. Study Objectives**

#### **3.1. Primary Objective**

To evaluate the effectiveness of Juvéderm® VOLIFT™ with Lidocaine for lip augmentation.

#### **3.2. Secondary Objective(s)**

To quantify the Investigators' and subject's assessment of aesthetic improvement of their lips.

#### **3.3. Brief Description**

This is a prospective, open-label, multi-center, interventional, medical device, post-marketing study evaluating the effectiveness of Juvéderm® VOLIFT™ with Lidocaine for lip augmentation. Subjects will attend up to 7 visits: Screening, Initial Treatment, Day 14 (touch-up, if required), Day 30, Month 3, Month 6, and Month 12 (study exit; see Figure 1). 60 subjects will be enrolled.

Eligible subjects will undergo treatment with Juvéderm® VOLIFT™ with Lidocaine administered via injection for enhancement as per the current directions for use (DFU)

[figure not shown]
[figure not shown]
[figure not shown]

Figure 1 Overall Study Design

### 3.4. Subject Selection

60 subjects will be treated in this study. Subjects who "drop out" after receiving treatment on Day 1 will not be replaced.

#### 3.4.1. Inclusion Criteria

The following are requirements for entry into the study.

1. Male or female, 18 years of age or older.
2. Signed the Institutional Review Board (IRB)/Independent Ethics Committee (IEC)-approved informed consent form prior to any study-related procedures being performed.
3. Accept the obligation not to receive any other facial procedures or treatments anywhere in the lower face (below the orbital rim), neck, and oral cavity at any time during the study that are not related to the study.

5. Women of childbearing potential must have a negative urine pregnancy test before each injectable treatment and practice a reliable method of contraception throughout the study.

6. Ability to follow study instructions and likely to complete all required visits and assessments, as assessed by the Investigator.

#### 3.4.2. Exclusion Criteria

2. Has lip tattoos or is planning lip tattoos during the course of the study, piercings, facial hair, or scars that would interfere with visualization of the lips and perioral area.
3. Has dentures or any device covering all or part of the upper palate, and/or severe malocclusion or dentofacial or maxillofacial deformities.
4. Has undergone oral surgery (e.g., tooth extraction, orthodontia, or implantation) within 6 weeks before

enrollment or is planning to undergo any of these procedures during the study.

5. Has ever undergone facial plastic surgery or received permanent facial implants (e.g., polymethylmethacrylate, silicone, polytetrafluoroethylene) anywhere in the face or neck, or is planning to be implanted with any of these products during the study.
6. Has undergone semi-permanent dermal filler treatment (e.g., hyaluronic acid, calcium hydroxylapatite, poly-L-lactic acid) in the lower face (below the orbital rim) within 24 months before enrollment or is planning to undergo such treatment during the study.
7. Has undergone mesotherapy or cosmetic resurfacing (laser, photo-modulation, intense pulsed light, radiofrequency, dermabrasion, chemical peel, or other ablative or non-ablative procedures) anywhere in the face or neck, or Botulinum toxin injections in the lower face (below the orbital rim) within 6 months before enrollment or is planning to undergo any of these procedures during the study.
8. Has used any lip plumping products within 10 days before enrollment or is planning to use such products during the study (study treatment may be delayed as necessary to accommodate this 10-day washout period).
9. Has begun using any over-the-counter or prescription, oral or topical, anti-wrinkle products for the lips or around the mouth within 90 days before enrollment or is planning to begin using such products during the study (subjects who have been on a regimen of such products for at least 90 days are eligible for the study if they intend to continue their regimen throughout the study).
10. Is on an ongoing regimen of anti-coagulation therapy (e.g., warfarin) or non-steroidal anti-inflammatory drugs (NSAIDs) (e.g., aspirin, ibuprofen) or other substances known to increase coagulation time (e.g., herbal supplements with garlic or gingko) within 10 days of undergoing study device treatment (study treatment may be delayed as necessary to accommodate this 10-day washout period).
11. Is on a concurrent regimen of lidocaine or structurally related local anesthetics (e.g., bupivacaine.)
12. Has a history of anaphylaxis, atopy, or allergy to lidocaine, hyaluronic acid (HA) products, or Streptococcal protein, or is planning to undergo desensitization therapy during the study.
13. Has an active inflammation, infection, cancerous or precancerous lesion, or unhealed wound in the mouth area.
14. Has porphyria.
15. Has epilepsy.
16. Has impaired cardiac conduction, severely impaired hepatic function, or severe renal dysfunction.
17. Has any uncontrolled disease.
18. Females who are pregnant, nursing, or planning a pregnancy.
19. Current enrollment in an investigational drug or device study, participation in such a study within 6 weeks before enrollment, or be planning to participate in another investigation during the course of this study.
20. Is an employee (or immediate relative of an employee) of the Investigator, Allergan, or a representative of Allergan.

### **3.5. Determination of Sample Size**

It is expected that the responder rate for this study is approximately 80% based on the results of a pivotal study of a similar investigational product Juvéderm Volbella XC. (See Geronemus *et al.*, 2018, unpublished manuscript). The margin of error (associated with 95% CI) for estimating an 80% expected responder rate is 10%, which is desirable to attain by having a sample size of 60 subjects for the study. Subjects' dropout rate is expected to be negligibly small at Day 30 post-treatment when the primary efficacy assessment is collected, thus 60 subjects will be recruited into the study.

### **3.6. Treatment Assignment & Blinding**

This is an open-label, single-arm study. Thus, blinding and randomization methods will not be implemented.

### **3.7. Administration of Study Medication**

[figure not shown]
The Investigator will determine the appropriate volume of Juvéderm® VOLIFT™ with Lidocaine to be injected to augment the lips (e.g., add fullness). It is anticipated that the volume of Juvéderm® VOLIFT™ with Lidocaine to be injected for lip augmentation will not exceed 3.0mL total per subject.

### **3.8. Study Procedures and Flowchart**

#### **3.8.1. Washout of Prohibited Medications/Treatments**

If washout of any medications is required, the subject must provide written informed consent before the washout can commence. Table 1 lists the medications/treatments that are prohibited during the study and the length of time that must pass between the medication/treatment and treatment in the study.

[figure not shown]
Study treatment may be delayed as necessary to accommodate the washout period. If treatment is delayed beyond the 14-day screening period (see Table 2: Schedule of Visits and Procedures), screening procedures are to be repeated as necessary to confirm participation eligibility. The inclusion/exclusion criteria must be reassessed and the subject eligibility confirmed prior to study treatment.

### 3.8.2.      Unscheduled Visits

[figure not shown]
Each time the subject returns to the study center, the investigator (or designee) will solicit and record information about injection site reactions (ISRs), adverse events (AEs), and concomitant medications/procedures. An interim or unscheduled visit may replace a scheduled visit if it occurs within the acceptable visit window for a scheduled visit or if the scheduled visit was missed. All applicable procedures should be performed.

### 3.8.3.      Flowchart

[figure not shown]
This document is [REDACTED]

[figure not shown]

This document is [REDACTED]

[REDACTED]

This document is [REDACTED]

## 4. Endpoints

### 4.1. Primary Efficacy Endpoint

The primary endpoint will be the responder rate for lip fullness on the LFS2, which is defined as the proportion of subjects who show  $\geq 1$ -point improvement on the LFS2 compared to baseline assessment, at Day 30 after last treatment received.

### 4.2. Secondary Efficacy Endpoints

#### 4.2.1. Oral Commissures Severity Scale (OCSS)

Change from baseline in OCSS will be determined at each post-treatment visit.

#### 4.2.2. FACE-Q™ – Satisfaction with Lips Questionnaire

Subject's assessment of satisfaction with treatment of their lips as measured by the change from baseline in the FACE-Q™ Satisfaction with Lips questionnaire at all post-treatment visits.

#### 4.2.3. Global Aesthetic Improvement Scales (GAIS)

- Investigator's assessment of global facial aesthetic improvement as measured by the 5-point GAIS at post-treatment visits beginning at Day 30 after last treatment received.
- Subject assessment of global facial aesthetic improvement as measured by the 5-point GAIS at post-treatment visits beginning at Day 30 after last treatment received.

#### 4.2.4. Natural Look and Feel/Product Smoothness/Dynamic Lip Lines

- Subject's assessment of natural look and feel of their lips as measured by the 5-point Likert scale at post-treatment visits beginning at Day 30 after last treatment received.
- Investigator's assessment of product smoothness as measured by the 5-point Likert scale at post-treatment visits beginning at Day 30 after last treatment received.
- Investigator assessment of dynamic lip lines upon animation at post-treatment visits beginning at Day 30 after last treatment received

## 5. Analysis Sets

The primary analysis set to be used for the analysis of the efficacy data will be the Evaluable Set (ES).

### 5.1. Screened Set

The Screened Set will include all subjects entered into the study (See Section 6.2 for definition of 'entered'). Unless specified otherwise, this set will be used for subject listings and for summaries of subject disposition.

### 5.2. Full Analysis Set

The Full Analysis Set (FAS) will include all subjects who were consented and enrolled into this study (See Section 6.2 for definition of 'enrolled'). The FAS will be used to summarize major protocol deviations (PDs) and for all efficacy data listings.

### 5.3. Safety Analysis Set

The Safety Analysis Set (SS) is identically defined to the FAS. The SS will be used for all analyses of safety endpoints.

### 5.4. Evaluable Set

The ES will include all subjects in the FAS who have had at least a baseline and a Day 30 (Visit 3) post-treatment efficacy assessment. The ES will be used for all analyses of efficacy endpoints. This will be the primary analysis set for analysis of the primary endpoint.

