### 5.5. Per Protocol Set

The Per Protocol Set (PPS) will include all subjects in the ES who had not had any major protocol deviations. The PPS will be used to corroborate the results from the ES for the primary endpoint. Criteria for exclusion from the PPS will include the following important PDs:

- Use of a prohibited medication.
- Use of prohibited concomitant procedures.
- Violation of key inclusion or exclusion criteria.
- Violation of follow-up, or significant deviation from defined visit windows.

Subjects will be assigned to the PPS by Allergan by reviewing PDs as detailed in Section 5.6.

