### 6.3. Missing Data

No imputation of missing data will be made for any of the outcome variables.

For the purpose of assigning treatment-emergent AEs (TEAEs), prior and concomitant medications, and prior and concomitant procedures, the followings rules will be applied for partial or missing start dates:

- If the day is missing, the first day of the given month will be used unless the month and year are the same as the month and year of enrollment, in which case the date of enrollment will be used.
- If the day and month are missing, the 1st of January will be used unless the year is the same as the year of enrollment, in which case the date of enrollment will be used.

- If the whole date is missing, the date of enrollment will be used.

Imputed dates will not be displayed in data listings.

Other dates will not be imputed.

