## 7. Demographic, Other Baseline Characteristics and Medication

### 7.1. Subject Disposition and Withdrawals

The number of subjects entered and the number and percentage of subjects enrolled, completed and discontinued, together with the reasons for discontinuation will be summarized for the Screened Set. Disposition details and inclusion and exclusion criteria not met will be listed for the Screened Set.

The number and percentage of subjects included in, and reasons for exclusion from, each of the analysis sets will be presented for the Screened Set. Exclusions from analysis sets will be listed for the Screened Set.

No formal statistical testing will be carried out on these data.

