### 8.1. Primary Efficacy Endpoint and Analysis

The primary efficacy endpoint is the responder rate for lip fullness on the LFS2, which is defined as the proportion of subjects who show  $\geq 1$ -point improvement on the LFS2 compared to baseline assessment, at Day 30 after last treatment received.

The LFS2 is an Investigator assessment of overall lip fullness measured by a 5-point scale (see Table 4: Lip Fullness Scale 2 (LFS2)). The investigator will use the LFS2 to perform a live assessment of the subject at the visits specified in Table 2, Schedule of Visits and Procedures. Improvement will be calculated as post-treatment LFS2 score – baseline LFS2 score.

The LFS2 score at baseline and at Visits 3, 4, 5, and 6 as well as the improvement from baseline at all post-treatment visits and the responder rate for lip fullness on the LFS2 at Day 30 will be summarized using summary statistics for categorical data for the ES, and also for the PPS as a supportive analysis. LFS2 grades, scores and improvements from baseline will be listed for the FAS.

Table 4 Lip Fullness Scale 2 (LFS2)

Grade	Description	Score
Very Marked	Very significant red lip show, lower lip pout, and upper lip pout	4
Marked	Significant red lip show and lower lip pout	3
Moderate	Moderate red lip show with slight lower lip pout	2
Mild	Some red lip show; no lower lip pout	1
Minimal	Flat or nearly flat contour, minimal red lip show	0

Photographic images will be collected to capture the subject status at the time of the live assessments. Facial photographs will be captured prior to study treatments and immediately after. Additional images will be captured at the Day 30, Month 3, Month 6, Month 12 and any subsequent visits. Images will be used by the investigator and subject for the facial assessments. 3D photographs will also be taken for each subject to aid in facial assessments and measure the volume change in the lips. Photograph collection details will be listed only for the FAS.

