## 15. Index of Tables

Header	Table Number	Name	Analysis Set
14.		Tables, Figures, and Graphs Referred to but not Included in the Text	
14.1		Demographic Data Summary Tables	
14.1.1		Subject Disposition	
	14.1.1	Number of Subjects Enrolled and Study Termination	Screened Set
14.1.2		Protocol Deviations	
	14.1.2.1	Major Protocol Deviations	Full Analysis Set
	14.1.2.2	Reasons for Exclusion from Analysis Sets	Screened Set
14.1.3		Demographic and Baseline Characteristics	
14.1.3.1		Subject Demographic and Baseline Characteristics	
	14.1.3.1.1	Subject Demographic and Baseline Characteristics	Safety Analysis Set
	14.1.3.1.2	Subject Demographic and Baseline Characteristics	Evaluable Set
	14.1.3.1.3	Subject Demographic and Baseline Characteristics	Per Protocol Set
14.1.3.2		Baseline Characteristics	
	14.1.3.2.1	Fitzpatrick Skin Phototype	Safety Analysis Set
	14.1.3.2.2	Fitzpatrick Skin Phototype	Evaluable Set
	14.1.3.2.3	Fitzpatrick Skin Phototype	Per Protocol Set
14.1.3.3		Medical History	
	14.1.3.3	Medical History	Safety Analysis Set
14.1.4		Medications	
	14.1.4.1	Prior Medications	Safety Analysis Set
	14.1.4.2	Concomitant Medications	Safety Analysis Set
14.2		Efficacy Data Summary Tables	
14.2.1		Primary Efficacy Parameter Responder Rate for Lip Fullness on the LFS2	
	14.2.1.1	Primary Efficacy Parameter Responder Rate for Lip Fullness on the LFS2: Primary Analysis	Evaluable Set
	14.2.1.2	Primary Efficacy Parameter Responder Rate for Lip Fullness on the LFS2: Secondary Analysis	Per Protocol Set
14.2.2		Secondary Efficacy Parameters	
	14.2.2.1	Secondary Efficacy Parameter 1 Oral Commissures Severity Scale (OCSS)	Evaluable Set
	14.2.2.2	Secondary Efficacy Parameter 2 FACE-Q – Satisfaction with Lips Questionnaire	Evaluable Set
	14.2.2.3	Secondary Efficacy Parameter 3 Investigator's Assessment of Global Facial Aesthetic Improvement	Evaluable Set
	14.2.2.4	Secondary Efficacy Parameter 4 Subject Assessment of Global Facial Aesthetic Improvement	Evaluable Set

Header	Table Number	Name	Analysis Set
	14.2.2.5	Secondary Efficacy Parameter 5 Subject's Assessment of Natural Look and Feel of Their Lips	Evaluable Set
	14.2.2.6	Secondary Efficacy Parameter 6 Investigator's Assessment of Product Smoothness	Evaluable Set
	14.2.2.7	Secondary Efficacy Parameter 7 Investigator Assessment of Dynamic Lip Lines Upon Animation	Evaluable Set
14.3		Safety Data Summary Tables	
14.3.1		Adverse Events	
	14.3.1.1	Treatment-emergent Adverse Events – Overall Summary	Safety Analysis Set

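### No planned table reports the Day 30 responder rate in all treated subjects, and the only supportive set cannot show the effect of leaving subjects out of the primary one

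*SAP*

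**What the plan says.** SAP 5.4 limits the ES to FAS subjects "who have had at least a baseline and a Day 30 (Visit 3) post-treatment efficacy assessment" and makes it the primary set for the primary endpoint. The PPS in SAP 5.5 "will include all subjects in the ES who had not had any major protocol deviations". SAP 8.1 states that the LFS2 results, including the Day 30 responder rate, "will be summarized using summary statistics for categorical data for the ES, and also for the PPS as a supportive analysis". The table index agrees:

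- Table 14.2.1.1, "Primary Efficacy Parameter Responder Rate for Lip Fullness on the LFS2: Primary Analysis", is for the ES.
- Table 14.2.1.2, "Primary Efficacy Parameter Responder Rate for Lip Fullness on the LFS2: Secondary Analysis", is for the PPS.
- No responder table is listed for the FAS.

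Under SAP 5.2 and 6.2 the FAS is everyone who was treated. Its role is stated in one sentence: "The FAS will be used to summarize major protocol deviations (PDs) and for all efficacy data listings". SAP 6.3 adds: "No imputation of missing data will be made for any of the outcome variables". SAP 7.1 does provide for "The number and percentage of subjects included in, and reasons for exclusion from, each of the analysis sets", so the size of each set will be reported.

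On timing, SAP 6.2 gives Visit 3 as study day 30 +/- 7, or 44 +/- 10 after a touch-up. SAP 3.8.2 and protocol 6.2.8 let an unscheduled visit stand in for a scheduled one if it falls in the window or, alternatively, if the scheduled visit did not take place. SAP 6.4 (Visit Windows) is marked as not applicable.

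**The concern.** The study has one arm and is descriptive, so the responder rate is the main result and there is no control group in which the same exclusions would also occur. The clinical hypothesis in protocol 2.2 is about subjects treated, and treated subjects who drop out are not replaced. Missing Day 30 data could be related to outcome. Protocol 8.2.1, for example, requires discontinuation of a subject who has repeat treatment outside the study's own touch-up or retreatment, and a poor result could prompt that. If the missing subjects respond less often, the ES rate is too high.

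A supportive analysis should vary the assumption that could be wrong. Moving from the ES to the PPS removes more subjects and brings none back, so agreement between Tables 14.2.1.1 and 14.2.1.2 says nothing about the subjects left out of both.

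The lesser matter is timing. The endpoint is defined 30 days after the last treatment, but the visible replacement rule sets no day limit when the scheduled visit was missed.

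**Working it through.** **Step 1. The plan's own figure.** Inputs from SAP 3.5: p = 0.80, n = 60. The 95% half-width is 1.96 × sqrt(0.80 × 0.20 / 60) = 0.101. The stated 10% margin is reproduced and is not in dispute.

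**Step 2. The sets.** PPS ⊆ ES ⊆ FAS = all treated. Responder tables exist for the two inner sets only, so no planned comparison involves the subjects who are in the FAS but not in the ES.

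**Step 3. Size, from an assumed truth.** The documents give no number missing at Day 30, so 1 and 3 are illustrative. Assume 48 of 60 true responders (the plan's 80%).

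| Missing | Their true status | ES rate | Shift from 80.0% | FAS, missing = non-response | FAS, missing = response |
|---|---|---|---|---|---|
| 0 | – | 48/60 = 80.0% | 0 | 80.0% | 80.0% |
| 1 | non-responder | 48/59 = 81.4% | +1.4 | 48/60 = 80.0% | 49/60 = 81.7% |
| 1 | responder | 47/59 = 79.7% | -0.3 | 47/60 = 78.3% | 48/60 = 80.0% |
| 3 | all non-responders | 48/57 = 84.2% | +4.2 | 48/60 = 80.0% | 51/60 = 85.0% |
| 3 | all responders | 45/57 = 78.9% | -1.1 | 45/60 = 75.0% | 48/60 = 80.0% |

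The two FAS figures bracket the true 80.0% in every row. They lie 1/60 = 1.7 points apart with one missing and 3/60 = 5.0 points apart with three.

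**Step 4. The same question from the reported side.** If the ES rate comes out at 80% and m subjects are missing, the FAS rate with missing as non-response is 0.80 × (60 - m)/60. That is 78.7% for m = 1, 76.0% for m = 3 and 72.0% for m = 6, or about 1.3 points per missing subject.

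**Step 5. Can a reader recover the bounds?** Largely, yes. The lower bound is ES responders / FAS N. The upper bound is (ES responders + subjects excluded from the ES) / FAS N. The inputs are the set counts under SAP 7.1 and Table 14.2.1.1. One gap remains: SAP 5.4 requires an efficacy assessment without naming LFS2, so an ES member could still lack an LFS2 value.

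**Step 6. Timing.** With 60 subjects, each off-time reading whose responder status differs from the Day 30 status moves the rate by 1/60 = 1.7 points. Before any window can be applied, the day count must be fixed:

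- Last treatment as day 1: days 23 to 37 are 22 to 36 days elapsed. Without touch-up this is study day 1 + 22 = 23 to 1 + 36 = 37, which matches 30 +/- 7. With touch-up 11 to 17 days after Visit 1 it is 1 + 11 + 22 = 34 to 1 + 17 + 36 = 54, which matches 44 +/- 10.
- The same count, but with Visit 2 read as study day 14 +/- 3 (10 to 16 days after Visit 1): 1 + 10 + 22 = 33 to 1 + 16 + 36 = 53, which does not match.
- Last treatment as day 0 (23 to 37 days elapsed): without touch-up, study day 24 to 38, which does not match.

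Protocol section 3 places the visit 30 days after the last treatment, while day 30 under the day 1 count is 29 days elapsed. The documents do not settle the convention.

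**The case against.** The best defence of the plan is that the ES is pre-specified, the study is descriptive, and SAP 3.5 expects Day 30 dropout to be negligibly small. If nobody is missing, Table 14.2.1.1 is the all-treated table. The bounds follow from planned output, and FAS listing 16.2.6.1 shows the individual LFS2 values. Even the +4.2 points needs three missing subjects, all non-responders, and is under half the 10.1-point margin. If missing subjects respond at the same 80%, the expected bias is zero. All of this stands, and it limits the point to a modest gap in reporting. It does not answer the structural problem that the chosen supportive set cannot test the exclusions.

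A reader might infer more than the documents support:

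- **That the primary rate is biased or the ES is the wrong primary set.** Nothing shows that subjects will be missing, or that those missing would respond differently.
- **That the all-treated result is concealed.** It can be derived; it is only not committed to.
- **That the plan has no limit on late replacement visits.** The visit schedule, the body of the protocol's Day 30 visit section and the table shells are not shown, and any of them may set one. The PPS also screens significant window deviations. A defect in timing is therefore not established.
- **That late replacement readings should be dropped from the primary rate.** This would enlarge the group without a Day 30 value. ES membership needs a Day 30 assessment and the ES governs all efficacy analyses, so it could also remove those subjects from every efficacy table. If out-of-window scheduled readings were kept, like readings would be treated differently.

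**Conclusion.** The point holds as a gap in the supportive analysis. The Day 30 responder rate is planned for the ES and a subset of it only, outcomes are not imputed, and no planned table reports the rate in all treated subjects. The size depends on the number missing at Day 30, which the documents do not give: zero if none, and with three missing between -1.1 and +4.2 points, assuming 48/60 true responders. The likely effect is small. The case for acting is that the change costs little and settles the matter before the data are read. On timing, the conclusion is narrower: the visible text leaves the rule open, and a cross-reference would close it.

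**What to change.** Keep the ES as the primary set and leave its membership unchanged.

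1. **SAP 8.1 and the table index.** Add one supportive Day 30 responder table for the FAS, with missing LFS2 counted as non-response and the best-case bound (missing = response) beside it. State that it is by gender and overall only, because SAP 6.6 and 8 would otherwise repeat it across every subgroup.
2. **SAP 6.4.** Replace the not-applicable entry with a pointer to the Visit 3 window in SAP 6.2, or to the visit schedule if that sets the limit, and state how days are counted from the last treatment.
3. **Same table.** Show the FAS rate again with all out-of-window Day 30 readings set to missing, treating scheduled and replacement visits alike. Remove no reading from the primary rate.

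The cost is one table and a few sentences. No new data are needed, and visit conduct and the protocol do not change. The downside is a supportive rate that may look slightly less favourable than the primary one.
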